Several recently completed non-clinical studies support the proposed Cohort 2 dose and dosing regimen. A recently completed 27-week dose-response good laboratory practice (GLP) toxicology study in non-human primates assessed the long-term safety, toxicology, and toxicokinetics of weekly doses of SYNT001. Twenty-seven (27) once weekly 10-minute infusions of SYNT001, at doses of 5, 30, or 100 mg/kg, to cynomolgus monkeys was associated with non-adverse test article-related clinical effects and clinical pathology observations at  $\geq 5$  mg/kg. SYNT001 produced dose-dependent reduction of serum IgG levels without affecting IgA, IgM or albumin levels. The NOAEL of SYNT001 was 100 mg/kg following 17 infusions and 30 mg/kg following 27 infusions.

As indicated above, in the recently completed Phase 1a healthy male volunteer study, single doses of SYNT001 up to and including 30 mg/kg have been well tolerated. There were no dose limiting toxicities (DLTs), serious adverse events (SAEs), or any other safety concerns identified. No adverse events (AEs) were observed in the 1 and 3 mg/kg dose cohorts. The only moderate (Grade 2) AE observed was a single instance of headache in the 10 mg/kg cohort. Other subjects had mild (Grade 1) AEs at 10 mg/kg. In Cohort 4 (30 mg/kg), five subjects received SYNT001. All five subjects experienced AEs; all were mild (Grade 1), transient and resolved spontaneously without intervention. The most commonly reported AEs were headache.

A preliminary assessment of safety was conducted by SYNT001 Pemphigus Study SYNT001-103 Dose Escalation Committee (DEC). Seven subjects with pemphigus were treated with

10 mg/kg IV weekly doses over a period of 5 weeks. Overall, SYNT001 10 mg/kg IV was well tolerated. Headache (Grade 1 or 2, self-limited) was the only drug-related AE that was reported in more than one subject. Total IgG and CIC biomarkers were reduced by 59% and 50% respectively, from baseline levels following the fifth dose, returning to baseline within 1 to 2 months. Additionally, preliminary evidence of clinical efficacy as measured by a clinically validated scoring metric, the Pemphigus Disease Area Index, was observed across the population. The DEC approved a dose escalation of SYNT001 from 10 mg/kg IV weekly doses for 5 weeks to 30 mg/kg IV weekly doses for 5 weeks.

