**8.3.2 Cohort 2: Treatment Day 28**

For Cohort 2 Day 28 ( $\pm 3$  days), subjects will return to the clinic and the following procedures are to be performed prior to study drug infusion:

- Complete physical exam
- Vital sign measurements (sitting blood pressure, heart rate, respiratory rate, oral temperature) and pulse oximetry; to be measured immediately prior to the infusion
- Clinical safety laboratory tests (hematology, serum chemistry panel, urinalysis)
- Pregnancy test
- 12-lead ECG (to be obtained in triplicate after 5 minutes of rest in the supine position)
- Serum tetanus antibody and VZV antibody
- PDAI
- PK sample collection (collected just prior to the start of the study drug infusion)
- Immunogenicity sample collection (collected just prior to the start of study drug infusion)
- PD sample collection (collected just prior to the start of the study drug infusion)
  - IgG, IgG subtypes (IgG1-4), IgA, IgM
  - CIC
  - Anti-Dsg (1 and 3) antibody titers
  - C3
  - AECA
  - RNAseq
  - Immunophenotyping
  - Exploratory pemphigus immune response biomarkers
- Photography
- HR-QoL (ABQoL, Skindex-29)

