### **8.3.3 Cohort 2: Follow-up Day 112**

For Cohort 2 Day 112 ( $\pm$  5 days), subjects are to return to the clinic and the following procedures are to be performed:

- Vital sign measurements (after 5 minutes of rest; sitting blood pressure, heart rate, respiratory rate, oral temperature): abnormal results to be repeated after 5 minutes of rest
- Clinical safety laboratory tests (hematology, serum chemistry panel, urinalysis)
- PDAI
- Immunogenicity sample collection
- PD sample collection
  - IgG, IgG subtypes (IgG1-4), IgA, IgM
  - CIC
  - Anti-Dsg (1 and 3) antibody titers
  - C3
  - AECA
  - Exploratory pemphigus immune response biomarkers
- Photography
- Concomitant medication assessment
- AE assessment

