#### **8.4 All Cohorts: End of Study or Early Termination Visit; Cohort 1, Day 112; Cohort 2, Days 91 and 140**

For Cohort 1 Day 112 ( $\pm 5$  days) and Cohort 2 Days 91 and 140 ( $\pm 5$  days), subjects are to return to the clinic and the following procedures are to be performed:

- Complete physical exam
- Vital sign measurements (after 5 minutes of rest; sitting blood pressure, heart rate, respiratory rate, oral temperature): abnormal results to be repeated after 5 minutes of rest
- Clinical safety laboratory tests (hematology, serum chemistry panel, urinalysis)
- Pregnancy test
- 12-lead ECG (to be obtained in triplicate after 5 minutes of rest in the supine position) (*Cohort 2, Days 91 and 140 only*)
- Serum tetanus antibody and VZV antibody
- PDAI
- Immunogenicity sample collection
- PD sample collection
  - IgG, IgG subtypes (IgG1-4), IgA, IgM
  - CIC
  - Anti-Dsg (1 and 3) antibody titers
  - C3
  - AECA
  - RNAseq (*Cohort 1 Day 112; Cohort 2, Day 91 only*)
  - Urine IgG (*Cohort 1 only*)
  - Immunophenotyping (*Cohort 2, Day 91 only*)
  - Exploratory pemphigus immune response biomarkers
- Photography
- HR-QoL (ABQoL, Skindex-29) (*Cohort 2 only*)
- Concomitant medication assessment
- AE assessment

**Note:** a subject may choose to terminate participation in the study at any time. Under this circumstance, the subject will be encouraged to return as soon as possible for an early termination visit and to receive assessments otherwise scheduled on Day 112 (Cohort 1) or Day 91 (Cohort 2).

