## ABQOL Questionnaire

Name: \_\_\_\_\_ Date: \_\_\_\_\_

DOB: \_\_\_\_\_ Sex: M / F Contact Number: \_\_\_\_\_

- Pemphigus Subtype:  Pemphigus Vulgaris  Epidermolysis Bullosa Aquisita  
 Bullous Pemphigoid  Linear IgA Bullous Dermatoses  
 Pemphigus Follaceus  Mucous Membrane Pemphigoid  
 Other \_\_\_\_\_

The following questions ask about the ways in which *blistering disease treatments* affect your quality of life.

Please choose an option from the right hand column which most closely correlates to how you felt *within the last week*.

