**Thank you for taking the time to complete this questionnaire**

**APPENDIX 4. SKINDEX-29**

# DERMATOLOGY SURVEY

This survey concerns the skin condition which has bothered you the most during the past four weeks.

These questions concern your feelings over the past 4 weeks about **the skin condition that has bothered you the most**. Check the answer that comes closest to the way you have been feeling.

**HOW OFTEN DURING THE PAST FOUR WEEKS  
DO THESE STATEMENTS DESCRIBE YOU?**

NEVER      RARELY      SOMETIMES      OFTEN      ALL THE TIME

	NEVER	RARELY	SOMETIMES	OFTEN	ALL THE TIME
1. My skin hurts . . . . .	 1	 2	 3	 4	 5
2. My skin condition affects how well I sleep . . . . .	 1	 2	 3	 4	 5
3. I worry that my skin condition may be serious . . . . .	 1	 2	 3	 4	 5
4. My skin condition makes it hard to work or do hobbies . . . . .	 1	 2	 3	 4	 5
5. My skin condition affects my social life . . . . .	 1	 2	 3	 4	 5
6. My skin condition makes me feel depressed . . . . .	 1	 2	 3	 4	 5
7. My skin condition burns or stings . . . . .	 1	 2	 3	 4	 5

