**APPENDIX 5. COHORT 2 ALTERNATE SCHEDULE OF EVENTS TABLE**

**Table 10. Study Assessments for Cohort 2 (Alternate Weekly Dosing Option)**

Visit Number	Screening	Loading			Maintenance										Follow-Up		
	1	2	3	4	5	6	7	8	9	10	11	12	13	14	15	16	17
Time Point (Study Day)	-14 to -1	0 Baseline	7 (±1 d)	14 (±1 d)	21 (±3 d)	28 (±3 d)	35 (±3 d)	42 (±3 d)	49 (±3 d)	56 (±3 d)	63 (±3 d)	70 (±3 d)	77 (±3 d)	84 (±3 d)	91 (±5 d) or ET Visit	112 (±5 d)	140 (±5 d) EOS Visit
Informed consent	X																
Demographics/medical history	X																
Inclusion/exclusion	X																
Physical examination a	X	X	X	X	X	X	X	X	X	X	X	X	X	X	X		X
Vital signs b	X	X	X	X	X	X	X	X	X	X	X	X	X	X	X	X	X
Pulse oximetry c		X	X	X	X	X	X	X	X	X	X	X	X	X			
Clinical safety labs d	X	X	X	X	X	X	X	X	X	X	X	X	X	X	X	X	X
Pregnancy test e	X	X			X										X		X
Hepatitis and HIV screen	X																
12-lead ECG f	X	X		X	X										X		X
Tetanus and VZV antibodies g		X			X										X		X
PDAI h	X	X	X	X	X	X	X	X	X	X	X	X	X	X	X	X	X
PK sampling i		X	X	X	X		X							X			
Immunogenicity j	X	X	X	X	X	X	X	X	X	X	X	X	X	X	X	X	X
Study drug administration k		X	X	X	X	X	X	X	X	X	X	X	X	X			
Immunoglobulins (IgG, IgA, IgM) and IgG subtypes (IgG1-4) l	X	X	X	X	X	X	X	X	X	X	X	X	X	X	X	X	X q
CIC		X	X	X	X	X	X	X	X	X	X	X	X	X	X	X	X
Anti-Dsg (1 and 3) antibody titers	X	X	X	X	X	X	X	X	X	X	X	X	X	X	X	X	X
C3 and AECA m	X	X	X	X	X	X	X	X	X	X	X	X	X	X	X	X	X
FCGR2A by buccal swab n		X															
RNA sequencing		X			X										X		
Immunophenotyping o		X			X										X		
Exploratory pemphigus immune response biomarkers		X	X	X	X	X	X	X	X	X	X	X	X	X	X	X	X

Photography p		X	X	X	X	X	X	X	X	X	X	X	X	X	X	X	X
HR-QoL assessments		X			X											X	X
Adverse events	To be collected from the date that the ICF is signed through the last study visit																
Concomitant medications	To be collected from within 14 days prior to Day 0 through the last study visit																

CIC = circulating immune complexes; d = day(s); ECG = electrocardiogram; EOS = end of study; ET= early termination; *FCGR2A* = Fc gamma R2a receptor; HIV = human immunodeficiency virus; HR-QoL = health-related quality of life; ICF = informed consent form; Ig = immunoglobulin; PDAI = Pemphigus Disease Area Index; PK = pharmacokinetic; VZV = varicella-zoster virus

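### In the weekly-dosing schedule (Table 10) the end-of-treatment quality-of-life mark sits at Day 112 instead of Day 91/ET, contradicting Sections 8.3.3 and 8.4 and Table 3

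*Protocol*

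**What the plan says.** The protocol gives the Cohort 2 quality-of-life timing (ABQoL and Skindex-29) in four places.

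- Table 3, every-other-week maintenance: Days 0, 28, 91 and 140.
- Appendix 5, Table 10, weekly maintenance, row "HR-QoL assessments": visits 2, 5, 16 and 17, which are Days 0, 21, 112 and 140. Visit 15, headed as Day 91 or the early-termination visit, has no mark.
- Section 8.4, covering Cohort 2 Days 91 and 140 and early termination, lists "HR-QoL (ABQoL, Skindex-29) (*Cohort 2 only" and makes no exception for weekly dosing. Its closing note sends Cohort 2 early terminators to the Day 91 assessments.
- Section 8.3.3, Cohort 2 Day 112, has no quality-of-life item in its procedure list.

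The recall periods are printed on the forms. Skindex-29 (Appendix 4) asks "HOW OFTEN DURING THE PAST FOUR WEEKS"; ABQoL (Appendix 3) asks how the subject felt "within the last week". Under Table 10 the last infusion is on Day 84. Section 7.12 asks for stable corticosteroids until two weeks after the last dose and permits a taper from then on. Section 3 makes quality of life an exploratory endpoint, summarized by dose, regimen and visit.

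**The concern.** The table and the text give a site different instructions for the same visits. A coordinator or an eCRF builder working from Table 10 would collect nothing at Day 91 or at early termination and would collect a form at Day 112 that the text does not ask for.

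Two things are at stake. First, the form meant to capture quality of life at the end of maintenance would instead be completed four weeks after the last infusion, when steroid changes are already permitted, so it answers a different question. Second, the endpoint is to be summarized by regimen and visit, yet after baseline the weekly and every-other-week schedules would coincide only at Day 140, well after treatment in both. A questionnaire not administered at Day 91 cannot be recovered later by any analysis.

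**Working it through.** The protocol states no figure to reproduce. The check is a column count followed by recall-window arithmetic.

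**Column count.** The quality-of-life row of Table 10 has all 17 visit cells, with marks in cells 2, 5, 16 and 17. The Table 3 row has 12 cells, with marks in cells 2, 5, 10 and 12. Comparing with rows that share the same pattern:

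| Row | Table 3 (days) | Table 10 (days) |
|---|---|---|
| Tetanus and VZV antibodies | 0, 28, 91, 140 | 0, 21, 91, 140 |
| RNA sequencing | 0, 28, 91 | 0, 21, 91 |
| Immunophenotyping | 0, 28, 91 | 0, 21, 91 |
| Quality of life | 0, 28, 91, 140 | 0, 21, **112**, 140 |

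The pregnancy test and ECG also keep their Day 91 marks in Table 10. Of the assessments grouped at visit 5 and the end of treatment, only quality of life leaves Day 91. In Table 3 its post-baseline pattern is the same as that of tetanus/VZV; in Table 10 it is one column to the right.

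**Does Section 8 apply to the weekly option here?** The follow-up visits are the same in both tables: Days 91, 112 and 140. Sections 8.3.3 and 8.4 therefore describe visits that exist in Table 10, and they conflict with it directly.

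**Recall windows.** The window runs from (visit day − recall length) to visit day. The last dose is Day 84.

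- Skindex-29 at Day 112: 112 − 28 = 84, so Days 84 to 112. None of the 28 days precedes the last dose at nominal timing.
- Effect of visit windows (Day 112 ± 5, Day 84 ± 3): the earliest visit is Day 107, and 107 − 28 = 79. That reaches 84 − 79 = 5 days before a Day 84 last dose, or 87 − 79 = 8 days before a Day 87 last dose. The maximum is 8.
- ABQoL at Day 112: 112 − 7 = 105, so Days 105 to 112. Even at Day 107 the window starts at Day 100, after the latest possible last dose (Day 87).
- At Day 91, for comparison: Skindex-29 covers Days 63 to 91, of which 84 − 63 = 21 of 28 days run up to the last dose. ABQoL covers Days 84 to 91, one weekly dosing interval after the last infusion.

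**Steroids.** A taper is permitted from 84 + 14 = Day 98. Day 91 falls before that at nominal timing and Day 112 falls after it. Of the Day 112 Skindex-29 window, 112 − 98 = 14 of 28 days lie in the taper-permitted period; the whole ABQoL window does.

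**Overlap of schedules.** {28, 91, 140} and {21, 112, 140} share only Day 140. With the mark at Day 91 they would share Days 91 and 140.

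**The case against.** Several points on the other side have force.

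A reader might infer that the Day 21 mark is also wrong and belongs at Day 28, since Table 3 and Section 8.3.2 place it there and a four-week Skindex-29 recall at Day 21 reaches back to Day −7 (7 of 28 days before the first dose). The documents do not support calling that an error. Visit 5 is the first maintenance dose in both tables, and the pregnancy test, visit-5 ECG, tetanus/VZV, RNA sequencing and immunophenotyping all move to Day 21 with quality of life, which looks deliberate. Sections 8.3.1 and 8.3.2 list only the every-other-week treatment days, so they cannot contradict Table 10 on which treatment visit carries the forms. ABQoL at Day 21 covers Days 14 to 21, all on treatment.

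A reader might also infer that early terminators on weekly dosing will give no quality-of-life data. That assumes the table overrides Section 8.4, which requires the form. What can be said is that the instructions conflict and the form may be missed.

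It would also be too strong to argue that the drug effect has worn off by Day 112. The statement that IgG and immune-complex levels were reduced "from baseline levels following the fifth dose, returning to baseline within 1 to 2 months" comes from five weekly doses of 10 mg/kg, a different regimen, and it does not concern quality of life.

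Finally, the endpoint is exploratory and descriptive, no formal comparison of regimens is stated, and weekly dosing is only an option. That limits the importance but does not remove the contradiction at Days 91 and 112.

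**Conclusion.** The point stands as a genuine but minor inconsistency. Table 10 places the end-of-treatment quality-of-life form at Day 112, where Section 8.3.3 has none, and omits it at Day 91/ET, where Section 8.4 and Table 3 have it. Because every other assessment in the same group stays at Day 91, a misplaced mark is the likeliest explanation.

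If Table 10 is followed, the end-of-treatment form is replaced by one taken 28 days after the last dose. At nominal days its Skindex-29 recall lies wholly after the last dose (visit windows can admit up to 8 earlier days), and its ABQoL recall lies wholly after it in any case. The two schedules then have only Day 140 in common after baseline.

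This affects only subjects on the weekly option, out of at most 12 in Cohort 2, and only an exploratory endpoint. It rests on the table columns having been read correctly from the PDF. The row has its full 17 cells and aligns with its neighbours, so a reading error is unlikely.

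**What to change.** In Table 10, move the quality-of-life mark from visit 16 (Day 112) to visit 15 (Day 91 or early termination), so that it agrees with Sections 8.3.3 and 8.4 and with Table 3, and update the eCRF visit map to match. Leave the Day 21 mark where it is.

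The cost is one table cell and one entry in the visit map; no visit or form is added. If any subject has already followed Table 10 as printed, keep those forms under Day 112 in the summaries and do not relabel them as Day 91.

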## **BACKGROUND**

Protocol amendment Version 5.0 of the SYNT001-103 protocol was issued on 18 September 2018.

Syntimmune is amending the SYNT001-103 protocol to adjust the dosing schedule and cohort options. Because enrollment in Cohort 1 is complete, subjects will be enrolled in Cohort 2 which will now evaluate 3 weekly loading doses followed by 5 every other week maintenance doses, with the option to adjust to weekly dosing, if needed. Most updates in the amendment were incorporated to reflect this change, as well as refine how the ongoing safety of subjects in Cohort 2 would be monitored. The number of sites was increased to aid in enrollment and PDAI and photography assessments are now included at every post-treatment visit for Cohort 2 to better assess efficacy. PDAI also assessment added at screening for Cohort 2.

General grammatical, typographical, and formatting updates have been made throughout the document to provide consistency and clarity, reduce redundancy, and improve readability. These changes are not detailed in the summary below. Please see Amendment 5 for details.

**SUMMARY OF CHANGES**

With this update, the following changes since Version 4.0 have been made:

**Table 1. Summary of Changes: Protocol Version 5.0**

Section Number and Title	Description of Change
Sponsor Signature	The name of the Sponsor Representative has been updated.
Section 1, Protocol Synopsis	
Below is a summary of changes to the protocol synopsis; refer to the changes described for the individual protocol sections for more detail:
 
 
• Increased the number of study sites from 10 to 20 global sites to support subject enrollment.
 
• Study objectives and endpoints were updated to reflect changes to the dosing regimen (every other week in maintenance phase), to clarify that serum is used for pharmacokinetic analyses, and to update how analysis summaries will be presented.
 
• The Study design and Methodology sections have been merged.
 
• The Study design not only describes changes to cohorts but also includes the role of the Dose Escalation Committee (DEC), Sponsor Medical Lead, and stopping and dose escalation rules.
 
• The Number of subjects section has been updated to reflect the changes in the number of subjects and that Cohort 1 may enroll “up to” 8 subjects and Cohort 2 may enroll “up to” 12 subjects.
 
• The Study population section was modified to better define the population.
 
• Inclusion criterion #4a was updated to reduce the last previous dose of rituximab or other anti-CD20 monoclonal antibodies from >12 months to >9 months prior to screening.
 
• Inclusion criterion #9 was updated to reflect that male subjects are only required to use contraception through the final study visit.
 
• Exclusion criterion #12 was updated to specify “at screening.”
 
• Additional detail regarding dose/cohort changes has been added to Study drug, dosage, and administration and Duration of subject participation sections.
 
• More detail was added for clarity regarding corticosteroids.
 
• In the statistical consideration section, analyses have been updated to reflect changes to the dosing regimen (every other week in maintenance phase) and to update how analysis summaries will be presented.
 

Study Diagram	Study Diagram has been added for clarity around the changes to study design and the reduction in the number of cohorts to 2.

	
 
• Cohort 2 has been modified to 3 weekly loading doses of 30 mg/kg followed by 5 every other week doses of 10 mg/kg and the number of subjects enrolled will be up to 12.
 
• The original Cohort 2 and optional Cohort 4 were removed.
 
• The Sponsor Medical Team will conduct the 24-hour and 7-day safety reviews for subjects in Cohort 2.
 
• Ongoing safety review may result in may modified dosing regimen (e.g. 10 weekly maintenance doses at 10-30 mg/kg).
 

Schedule of Events	
Tables 3 and 4 (original Cohort 2 and Cohort 3) were deleted.
 
Table 3 (Cohort 2): This table reflects a new dosing schedule with loading and maintenance doses, as well as the increase of PDAI and photography assessments to every post-treatment visit. PDAI also added at screening. See Table 3 for details.

List of Abbreviations	
The table was updated to include all abbreviations throughout the synopsis and protocol text. Each abbreviation was defined the first time used in both the synopsis and protocol text.

Section 2, Background and Rationale	
Background and Rationale
 
 
• Text has been added to describe SYNT001's predicted mechanism of action
 
• Additional indications identified as IgG-mediated autoimmune disorders have been removed
 
 
Selection of Doses in this Study
 
 
• Details of mathematical modeling of study dose selection were added.
 
• Details of non-clinical and clinical studies supporting the proposed Cohort 2 dose and dosing regimen were added.
 

Section 3, Study Objectives and Endpoints	
 
• Study objectives and endpoints were updated to reflect changes to the dosing regimen (every other week in maintenance phase), to clarify that serum is used for pharmacokinetic analyses, and to update how analysis summaries will be presented.
 
• The secondary objectives were reordered to reflect their importance.
 

Section 4, Study Drug	
Description of SYNT001
 
 
• Added that Investigators are allowed to adjust the duration of the infusion to increase tolerability up to 4 hours, if needed.
 
 
Dose Requirements
 
 
• It has been clarified that subject doses will be limited to 5000 mg. A subject with a body weight that extrapolates to a dose > 5000 mg, will only receive 5000 mg.
 

Section 5, Study Design	
The number of study sites was increased from 10 to 20.
 
The study design has been updated to reflect changes in dosing regimen for Cohort 2.
 
 
• Cohort 1 number of subjects has been modified from 8 to up to 8.
 

	
 
• Cohort 2 has been modified to 3 weekly loading doses of 30 mg/kg followed by 5 every other week doses of 10 mg/kg and the number of subjects enrolled will be up to 12.
 
• Original Cohort 2 and optional Cohort 3 were removed.
 
• The Sponsor Medical Team will conduct the 24-hour and 7-day safety reviews for Cohort 2.
 
• Ongoing safety review may result in may modified dosing regimen (e.g. 10 weekly maintenance doses at 10-30 mg/kg).
 
• Duration of Subject Participation was added to the body of the protocol for consistency with the synopsis.
 

Section 6, Study Population
	
Target Population
 
 
• Based on the new study design, the total number of subjects has been changed to a maximum of 20 subjects, but the number is not included in this section, just a description of the study population.
 
 
Inclusion Criteria
 
 
• Inclusion criterion #4a was updated to reduce the last previous dose of rituximab or other anti-CD20 monoclonal antibodies from >12 months to >9 months prior to screening.
 
• Inclusion criterion #9 was updated to reflect that male subjects are only required to use contraception through the final study visit.
 
 
Exclusion Criteria
 
 
• Exclusion criterion #12 was updated to specify “at screening.”
 


Section 7, Study Procedures
	
 
• References to specific days have been removed because of the addition of the separate Cohort 2 table and possibility of following the optional weekly schedule in Appendix 3.
 
• Virology assessments were removed from Table 6 because they are not included with clinical laboratory panels.
 
• PK parameters studied in Cohort 1 differ from (the) successive cohort(s) and which include maximum serum concentration of SYNT001 and the associated Tmax.
 
• Pharmacodynamic Assessment (Table 7) has been updated to include timing of testing for Cohort 2
 
• A subsection re: corticosteroid use was added for clarity.
 

Section 8, Study Assessments
	
Sections were edited to reflect the updates to assessments performed in the new schedule of events for Cohort 2. See Section 8 for details.

Section 9, Study Rules
	
Subject Withdrawal
 
 
• Details were added to distinguish between follow up assessments for subjects who prematurely discontinue study drug versus subjects who prematurely discontinue from the study.
 
• Details were added to specify which study visits the subject should be encouraged to attend in each case above.
 
 
Stopping Rules

	
 
• The description of dose escalation stopping rules now reflects that Cohort 2 will not be a dose escalation cohort.
 
• Decisions regarding study stopping rules originally to be made by the DEC were updated to be decided by the Sponsor Medical Lead.
 

Section 10, Evaluation of Safety	
No substantial changes were made to this section; only updates to abbreviations and minor corrections for consistency.
 
Warnings and Precautions
 
 
• Allowed vaccinations were updated to 28 days after the final dose of study drug rather than discretion of investigator.
 

Section 11, Statistical Considerations	
“Data” was updated to “analysis” in headings.
 
Details of analyses have been updated to reflect changes to the dosing regimen (every other week in maintenance phase) and to update how analysis summaries will be presented.
 
Safety Analysis
 
 
• More detail was added to the safety analyses to be performed.
 
• Relationship of adverse events (AEs) to study drug was defined as in the AE section (related/not related).
 
• The lab analyses were updated to be formed by a central laboratory.
 
 
Pharmacokinetic Analysis
 
 
• PK and PD analyses were moved to separate sections.
 
• Details were made more general to cover different analyses performed in the 2 cohorts.
 
 
Pharmacodynamic (PD) Analysis
 
 
• Details of the presentation of disease activity marker results were added.
 

Sections 12-14	No edits other than global changes mentioned below.
Appendix 5	Appendix was added to include an alternate schedule of events for Cohort 2 (weekly dosing)
Global Changes	
 
• Edits and formatting changes have been made throughout to improve clarity and readability.
 
• Typographical and formatting corrections as well as corrections for consistency have been made.
 

